APPENDIX XIII: LANGUAGE SCREENER – ENGLISH

Language Proficiency and Preference

How well do you speak English?

- Very Well
- Well
- Not well
- Not at all

2. What language do you prefer for health care?

(specify the language) _____

(If English, **NOT ELIGIBLE**)

(If Spanish, **ELIGIBLE**)

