[name]
[contact]
Email: [contact]

SITES PARTICIPATING IN THE STUDY

Participation in this study is limited to the following AMC centers.

Site performing participant survey methods:

Memorial Sloan Kettering Cancer Center

Department of Psychiatry & Behavioral Sciences
[name]
[name]

[figure not shown]
ANCHOR trial sites for participant referrals:

All interested sites that are participating in the AMC-A01 trial may participate if this protocol is determined to be exempt by the local IRB.

PROTOCOL SYNOPSIS

Title:	Development of a Health-Related Symptom Index for Spanish-Speaking Persons Diagnosed with and either Treated or Monitored for Anal High-Grade Squamous Intraepithelial Lesions (HSIL)
Phase of Study:	Observational
Participating Institutions:	This protocol will be conducted at Memorial Sloan Kettering Cancer Center (MSKCC) and will be open for participant referrals to MSK from participating ANCHOR sites.
Accrual Target:	Up to 40 participants
Population:	Participants who are Spanish-speaking with limited English proficiency (LEP), and who have been diagnosed with HSIL within the prior nine months will be recruited for all phases of ANCHOR HSIL HRQoL Index (HQI) development.
Regimen:	Procedures in this trial will be similar to the AMC-A02 protocol to validate the HQI instrument (anal Health-Related Symptom Index, or aHRSI) in the Spanish language, repeating phases 4-6 (cognitive interviews) with fluent Spanish speakers. This study will employ a translation of the current instrument being studied in English-speaking participants. 
• Cognitive Interviews in Spanish (Round 1): We plan to consent 20 Spanish speaking participants in order to complete 20 cognitive interviews for feedback on the initial Spanish-language aHRSI draft.• Cognitive Interviews in Spanish (Round 2): We will recruit up to 10 participants for this round with revised items tested in a second round of cognitive interviews with a smaller new cohort of HIV+ eligible participants.• Cognitive Interviews in Spanish (Round 3): We will recruit up to 10 participants for this round, if further refinements to the Spanish-language aHRSI are indicated from the second round.
Duration:	One interview session (approximately 45-60 minutes)

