2.3 Study Design and Rationale

The ANCHOR study presents a unique opportunity for the measurement of health-related quality of life (HRQoL) among those diagnosed with HSIL, as no measure currently exists that captures the symptoms and related experiences of living with or being treated for HSIL. HRQoL is a “multi-domain concept that represents the participant’s general perception of the effect of illness and treatment on physical, psychological, and social aspects of life.”¹⁰ Devising a symptom index, as opposed to developing a full HRQoL measure, is a pragmatic approach developed and recommended by HRQoL expert and study consultant [name] to address the short time frame for measure development and implementation in the ANCHOR trial, and as a solid first step in assessing symptoms and HRQoL in this context. An index is a compilation of symptoms and concerns and typically does not have the more complex subscale structure of existing HRQoL measures¹¹. An index has the benefits of being briefer than existing HRQoL measures (e.g., < 20 items vs. 40+ items) more focal, quicker to implement, and is supported by methodologies and findings from multiple studies of [name] research team¹². The AMC-A02 study developed a HRQoL Symptom Index for HSIL and its treatment in the HIV-infected population.¹⁸ This trial seeks to develop a Spanish-language version of the HRQoL Symptom Index, the anal Health-Related Symptom Index (aHRSI), among Spanish-speaking persons with limited English proficiency (LEP).

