This study adds a seventh phase to the development paradigm conducted with protocol AMC-A02, which will use the translated aHRSI in Spanish to complete cognitive interviews of Spanish-speaking participants. We will be conducting cognitive interviews (see Appendices [VI](#) and [VII](#)) of the finalized measure in Spanish (see Appendices [XI](#) and [XII](#)) to establish the content validity of the measure in Spanish. In addition to the cognitive interviews, we will collect a brief demographic form, and collect information on the participants preferred language and language proficiency (see Appendices [IX](#), [X](#), [XIII](#), and [XIV](#)) for each participant. We will enroll up to 40 eligible HIV-positive participants from participating ANCHOR sites using the same eligibility criteria as AMC-A02 phase 2 (except the age limit is lowered to 18 and the added criteria that Spanish be their first language as per self-report) over three rounds of cognitive interviewing, as was done for the English language version in AMC-A02 phases 4-6.¹⁸

- Cognitive Interviews in Spanish (Round 1): The process for conducting the cognitive interviews will be the same as for the English ones outlined above in Phase 4. We will plan to consent 20 Spanish speaking participants in order to complete 20 cognitive interviews.
- Cognitive Interviews in Spanish (Round 2): We will complete Phase 5 in Spanish in the exact same method as we did for the English version if it is necessary. If necessary, we will recruit up to 10 participants for this Phase 5 round.
- Cognitive Interviews in Spanish (Round 3): We will complete Phase 6 in Spanish in the exact same method as we did for the English version if it is necessary. If necessary, we will recruit up to 10 participants for this Phase 5 round.

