3.1 Eligibility Criteria

- 3.1.1 HIV-1 infection
- 3.1.2 Age 18 years or older. This age restriction is intended to enrich the study population at risk for cancer since anal cancer occurs only rarely under this age even among HIV-infected individuals. Less than 1% of anal cancers occur under the age of 35 years¹⁵.
- 3.1.3 Biopsy-proven anal HSIL within the prior nine months
- 3.1.4 Participant must have received anal HSIL treatment in the last nine months. If the participant's treatment plan is "observation," the participant must have been diagnosed with anal HSIL in the last nine months.
- 3.1.5 Life expectancy of greater than 5 years
- 3.1.6 Fluent in Spanish with limited English proficiency, per self-report

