3.2 Exclusion Criteria

Participants who do not fulfill the criteria as listed in Section 3.1 above, are ineligible. Additionally, the presence of any of the following conditions will exclude a participant from study enrollment:

- 3.2.1 History of anal cancer
- 3.2.2 Inability to understand a written consent form

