
3.4.1 Referral process

MSKCC will provide the participating sites with instructions on how to refer study participants. The referral process will include a list of site specific unique identification numbers that will be used for each participant referral. Referring sites will not collect any data and they will only be responsible for assuring eligibility of all participant referrals.

After confirming a participant's eligibility, the site physician or designee will provide an Information Sheet (Appendices I and II) about the study containing the MSK RSA contact information with the unique identification number on the Sheet. It will be up to the participant to initiate a call to the MSK RSA, although one or more sites may provide telephone access within their clinics for referred participants to call the MSKCC contact.

When a referred patient calls the MSK RSA and expresses interest in participating in the study and all questions are answered, the patient will be asked to provide the unique study ID and her/his name and telephone number(s) for the purpose of scheduling matters only. The patient will be offered an appointment date/time for

the interview to be held at MSK or completed over the phone. Once the scheduling is done but before the date of the interview, the RSA will call the referring site for that patient to confirm patient eligibility in cases where the referred patient is not calling directly from the referring site clinic. This is to assure verbally that the referred patient meets the eligibility requirements and is the same person referred by that site.

The MSKCC screening log for each participant will be destroyed once the participant has completed the interview, declined to participate further, or after three follow-up telephone calls when a missed or rescheduled interview appointment occurs for those participants agreeing to participate.

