APPENDIX XIV: LANGUAGE SCREENER – SPANISH

Dominio y preferencia de idioma

1. ¿Qué tan bien habla el inglés?

- Muy bien
- Bien
- No bien
- Para nada bien

2. ¿En qué idioma prefiere comunicarse para recibir su cuidado médico?

(Especifique el idioma) _____

(Si eligió inglés, **NO ES ELEGIBLE**)

(Si eligió español, **ES ELEGIBLE**)

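### The language screener decides eligibility on preferred language alone, so it passes fluent English speakers whom criterion 3.1.6 excludes

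*Protocol*

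**What the plan says.** The protocol describes the language requirement in three ways.

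- **Limited English proficiency.** Section 3.1.6 requires participants to be "Fluent in Spanish with limited English proficiency, per self-report". The population entry in the synopsis and the opening part of Section 2.3 describe the same group. Section 3.2 makes the criterion binding: "Participants who do not fulfill the criteria as listed in Section 3.1 above, are ineligible".
- **First language.** Later in Section 2.3, where the criteria are compared with those of AMC-A02, the addition for this study is given as "the added criteria that Spanish be their first language as per self-report". Section 3.1 has no such criterion.
- **Preferred language for care.** The screener has two questions. The first asks how well the person speaks English, with four answers: *Very Well*, *Well*, *Not well*, *Not at all*. No answer carries a consequence. The second asks "What language do you prefer for health care" (in the Spanish form, "En qué idioma prefiere comunicarse para recibir su cuidado médico"). Only here is a verdict printed: English means not eligible, Spanish means eligible. Both language versions carry the same rule.

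On who applies the criteria, Section 3.4.1 says: "Referring sites will not collect any data and they will only be responsible for assuring eligibility of all participant referrals". Sections 2.3 and 4.0 refer to the screener as a means of collecting information on each participant.

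**The concern.** Preferring Spanish for health care and having limited English are different attributes, and the form itself asks about them separately. Only the first question measures what 3.1.6 requires, yet only the second decides. Staff who follow the form as printed will pass bilingual people whom 3.1.6 excludes. Staff who follow 3.1.6 have no stated cut-off with which to overrule the form.

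The study's product is evidence of content validity in Spanish, drawn from item-by-item probing of 20 to 40 people. With no formal statistical analysis planned (Section 5.0), the make-up of that sample is the main design feature supporting the claim. If English-proficient bilinguals enter, the sample is no longer the one the protocol describes.

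**Working it through.** There is no power or sample-size figure to reproduce. The check lists every outcome the form can print and compares it with 3.1.6.

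**Inputs.** Question 1 has 4 answers, and question 2 has 2 answers with a printed verdict (Appendices XIII and XIV). The requirement comes from 3.1.6. Round sizes are 20 for Round 1 and up to 10 each for Rounds 2 and 3 (synopsis and Section 2.3).

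**Number of outcomes.** 4 × 2 = 8.

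| Question 1 answer | Prefers English: form says | Prefers Spanish: form says | Limited English under 3.1.6? |
|---|---|---|---|
| Very Well | not eligible | eligible | no, on any sensible cut-off |
| Well | not eligible | eligible | cannot be classified: no cut-off given |
| Not well | not eligible | eligible | yes |
| Not at all | not eligible | eligible | yes |

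**Effect of question 1.** Within each preference column the verdict is constant, so the proficiency answer changes the result in 0 of 8 outcomes.

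**Conflict with 3.1.6 among the 4 eligible outcomes.**
- If only *Very Well* falls outside limited proficiency: 1/4 = 25%.
- If *Well* also falls outside it: 2/4 = 50%.

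The range reflects the missing cut-off. It describes the form and does not estimate the share of participants affected.

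**Weight of one participant.** 1/20 = 5% of Round 1; 1/10 = 10% of a full Round 2 or Round 3.

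**The first-language test.** Neither screener question asks about first language, and neither do the demographic sheets (Appendices IX and X). No form shown can apply the criterion in Section 2.3. It also selects a different group: a person can have Spanish as a first language and speak English very well.

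**Extraction loss.** The English and Spanish forms show the same layout, with four unmarked answers to question 1 and the verdict under question 2. The body text gives no cut-off either. A conversion fault is therefore an unlikely explanation.

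**The case against.** The strongest reply is that 3.1.6 governs. Section 3.2 makes anyone who fails it ineligible, and a mark under one item of an appendix form does not displace that. On this reading the printed verdict belongs to question 2 alone, while question 1 records the self-report that 3.1.6 asks for. There are further safeguards. Sites must assure eligibility before referral. Study staff call the site before the interview to confirm it, unless the patient is calling from the clinic (Sections 3.4.1 and 7.1). A misclassified participant could be found afterwards from question 1. It can also be said that someone who prefers Spanish for care can judge whether Spanish items are clear, and that the primary objective does not mention limited English proficiency.

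Several of these points stand. 3.1.6 formally binds, the confirmation call is a real check, and the documents do not show that including some bilinguals would change any item. The first-language phrase appears in a background comparison and does not by itself rule out limited proficiency.

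They do not remove the conflict. Sites and callers are asked to confirm a criterion for which no threshold is given, while a form titled a screener gives an explicit and different verdict. If the form is only descriptive, its eligibility labels are wrong; if it decides eligibility, question 1 needs a rule. Either way the text needs correcting. Finding such participants later does not restore the stated population.

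The missing time point for applying the screener is a lesser matter. Sites receive separate referral instructions, and the silence would not be a fault on its own.

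**Conclusion.** The concern holds as an internal contradiction in the protocol. Followed as printed, the screener admits people whom 3.1.6 excludes, and Section 2.3 states a further criterion that Section 3.1 lacks. Between 1 and 2 of the 4 outcomes marked eligible conflict with 3.1.6. The lower figure assumes only that a person answering *Very Well* does not have limited proficiency; the upper figure assumes the same of *Well*.

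No expected number of affected participants can be given, because the protocol has no figure for bilingual referrals. No effect on the content of the index has been shown. The text should be corrected before enrolment; the contradiction does not invalidate the design.

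**What to change.** - Choose one language criterion and word it the same way in the synopsis, both places in Section 2.3, and 3.1.6. Either drop first language or add it to Section 3.1 together with a question that captures it.
- State in 3.1.6 which question 1 answers count as limited English proficiency. The sponsor sets the cut-off; at the least, *Very Well* should not qualify.
- In Appendices XIII and XIV, print the verdict against questions 1 and 2 jointly.
- While making these edits, it would help to name in 3.4.1 or 3.4.2 the step before the interview at which the screener is applied.

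The cost is a few lines in two appendices and about one sentence each in Sections 2.3, 3.1.6 and 3.4. Some referred bilinguals would be turned away, so accrual, planned at about 5 per month, may be slightly slower.

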APPENDIX XIV: LANGUAGE SCREENER – SPANISH

Dominio y preferencia de idioma

1. ¿Qué tan bien habla el inglés?

- Muy bien
- Bien
- No bien
- Para nada bien

2. ¿En qué idioma prefiere comunicarse para recibir su cuidado médico?

(Especifique el idioma) _____

(Si eligió inglés, **NO ES ELEGIBLE**)

(Si eligió español, **ES ELEGIBLE**)
